### **Specific goals:**

1. Identify patients with glucose intolerance and obesity who may enter the study.
2. To assess the effect at 12 months with treatment with metformin 1700 mg / d and lifestyle modifications on insulin resistance, pancreatic islet function, and cardiovascular function in a group of patients with mixed prediabetes and obesity.
3. To assess the effect at 12 months of treatment with the combination of linagliptin 2.5 mg / metformin 850 mg every 24 h + Empagliflozin 12.5 mg / metformin 850 mg every 24 h and lifestyle changes on insulin resistance, the function of Pancreatic islet and cardiovascular function in a group of patients with mixed prediabetes and obesity.

4. Evaluate and compare cardiovascular risk markers (TNF $\alpha$ , IL6, hsPCR) before and after treatments in the 2 study groups.
5. Compare insulin resistance and pancreatic islet function between the study groups at the end of the intervention.
6. Evaluate and compare glucose metabolism using OGTT at the beginning and end of treatment in the study groups.

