### **MATERIAL AND METHODS**

**Type of study:** Single Center Parallel Clinical trial, randomized, double blind

**Study universe:** Mexican patients with mixed prediabetes and obesity.

**Study population:** Mexican patients with mixed prediabetes and obesity, from the State of Guanajuato.

**Location:** Regional High Specialty Hospital of Bajío and Division of Health Sciences of the University of Guanajuato, León, Gto.

**Type of sampling:** Non-probabilistic, of consecutive cases.

**Sample size:** The sample size calculation was performed based on the formula to compare proportions. We expect that quadruple therapy (linagliptin + empagliflozin + metformin + lifestyle modifications), improve at least 75% the outcome variables (insulin resistance, pancreatic islet function and cardiovascular function), at 6 months of initiated the intervention, as long as the standard therapy (metformin + lifestyle modifications) achieves only 30% [69-71, 73], so that the study is designed to detect a minimum difference of 45% between the study groups with a type I (alpha) error of 0.05 and a sample power of 80%, and according to the following formula [108]:

$$n = \frac{(Z_{\alpha/2} + Z_{\beta})^2 p_1(1-p_1)(r + 1)}{(d)^2 r}$$

Where,

$$(Z_{\alpha / 2} + Z_{\beta})^2 = 7.9$$

p1 = proportion of individuals in the best treatment who did not achieve improvement = 0.25

p2 = proportion of individuals in the worst treatment who did not achieve improvement = 0.70

r = ratio of individuals in the treatment groups = 1

d = difference expected to be found = 0.45

n = 14 + 20% of losses = 17 patients per group

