## SELECTION CRITERIA

### Inclusion Criteria:

- Patients with prediabetes, defined for the existence impaired glucose tolerance (glucose between 140 and 199 mg/dL at the 2 hours of the Oral Tolerance Glucose Test (OGTT) with impaired fasting glucose (fasting glucose between 100 and 125 mg/dL)
- Patients who accept to participate in the study and sign the informed consent letter.

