## **VARIABLES**

### **INDEPENDENT VARIABLE**

#### **1) Intervention**

a. Measurement level: Qualitative nominal

b. Indicator:

1. A for the group receiving quadruple therapy (linagliptin + empagliflozin + metformin + lifestyle modifications)
2. B for the group receiving standard therapy (metformin + lifestyle modifications)

c. Conceptual definition: Therapeutic strategy whose purpose is to avoid alterations in glucose metabolism and progression to DM2, and reduce cardiovascular risk.

d. Operational Definition:

1. When patients receive 1 tablet of linagliptin 2.5mg / metformin 850mg every 24 hours + 1 tablet of empagliflozin 12.5mg / metformin 850mg every 24 hours + lifestyle modifications for 12 months
2. When patients receive 1 tablet every 12 hours of metformin 850 mg + lifestyle modifications for 12 months

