### **2) Glycosylated hemoglobin**

- a. Type of variable and level of measurement: Quantitative ratio
- b. Indicator: %
- c. Conceptual definition: Biochemical test indicating the degree of glycemic control during the last 3 months
- d. Operational definition: Glycosylated hemoglobin values measured at the beginning and end of the study by HPLC technique.

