### **3) Pancreatic beta cell function (Insulin Oral Disposition Index = IDOI)**

- a. Type of variable and level of measurement: Dependent, Quantitative of reason
- b. Indicator: pmol / mmol
- c. Conceptual definition: Pancreatic beta cell's ability to secrete enough insulin and maintain normal glucose levels
- d. Operational definition: Value obtained with glucose and insulin values during the OGTT by applying the following formula:  $(\Delta I_{0-30}) / (\Delta G_{0-30})$ , where  $(\Delta I_{0-30})$  = difference in the value of insulin measured at 0 and 30 minutes of the OGTT; and  $(\Delta G_{0-30})$  = difference in the glucose value measured at 0 and 30 minutes of the OGTT, which will be measured at the beginning and at the end of the intervention in each study group.

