## **STATISTIC ANALYSIS**

The data will be presented with descriptive statistics, mean and standard or median deviation and interquartile range, as well as percentages and incidence. For comparisons of numerical variables between the study groups, we will use Student's t if the distribution of the data follows a normal pattern, otherwise the Mann-whitney U test will be used; To compare qualitative variables we will use Chi square. Delta analysis will be performed for differences between groups. It will be considered significant when the value of p is  $<0.05$ . For the analysis and presentation of the data we will use the SPSS Version 15 and GraphPad Prism 5 programs.

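### Numerical outcomes get only unadjusted tests and an undefined delta analysis; ANCOVA on baselines already planned would cost at most about 4% in variance at 14 per arm and could gain much more

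*Combined protocol and SAP*

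**What the plan says.** The Statistic analysis section is the whole analysis plan. Numerical variables are compared between arms with Student's t "if the distribution of the data follows a normal pattern, otherwise the Mann-whitney U test will be used". Qualitative variables get chi-square. Then comes "Delta analysis will be performed for differences between groups", with no scale, time point, outcome list or test. The section does not say whether the t or Mann-Whitney test applies to final values or to changes, and no covariate-adjusted analysis appears anywhere in the documents.

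The Specific goals include "Compare insulin resistance and pancreatic islet function between the study groups at the end of the intervention"; goals 4 and 6 ask for before-and-after comparisons of inflammation markers and glucose metabolism.

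Baselines are planned. Patient Recruitment places the five-sample OGTT (glucose and insulin) at screening. It lists inflammation markers, DEXA and echocardiography ahead of the randomization step. The first beta-cell index is one "which will be measured at the beginning and at the end of the intervention in each study group", and the Matsuda index is treated likewise. HbA1c is described as "Glycosylated hemoglobin values measured at the beginning and end of the study by HPLC technique", but it is not in the list of pre-randomization tests.

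The sample size statement is "n = 14 + 20% of losses = 17 patients per group".

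**The concern.** With about 14 evaluable patients per arm, precision is scarce. A test on final values ignores the baseline. A test on change subtracts it in full, which adds noise when baseline and follow-up are weakly correlated. Which of the two is more precise depends on the baseline-to-follow-up correlation and on the ratio of the two SDs. The documents give neither, so the plan cannot know in advance which unadjusted test is better. ANCOVA estimates the weight for the baseline from the data and needs no such guess. Leaving delta undefined adds a second problem: two analyses are available for each outcome and neither is named as the deciding one.

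The point covers continuous outcomes with a baseline. It does not cover the yes/no glucose outcome (Dependent variables, item 1), the hyperglycemic clamp (first listed at the mid-term evaluation) or the endothelial markers (first listed at completion).

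**Working it through.** **The plan's own figure.** The formula under Sample size gives 7.9 × 0.25 × 0.75 × 2 / 0.45² = 14.63, stated as 14. Then 14 × 1.2 = 16.8, stated as 17. I use 14 analysed per arm.

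**Inputs.** n = 14 per arm and two-sided 0.05 come from Sample size. Two quantities are assumed, because the documents give neither: r, the baseline-to-follow-up correlation (0.3, 0.5, 0.8), and k, baseline SD divided by follow-up SD (0.5 to 1.5).

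**Variance of the arm difference, in units of the final-value variance:**
- final value: 1
- change score: 1 + k² − 2rk
- ANCOVA: (1 − r²) × [1 + 1/(2n − 4)]; at n = 14 the bracket is 25/24 = 1.042

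**Ceiling on the loss.** Since 1 + k² − 2rk = (k − r)² + (1 − r²), it is never below 1 − r². The ratio of ANCOVA to change is therefore at most 25/24, a 4.2% loss, whatever r and k are. Against final values the worst case is r = 0, with the same ceiling. The ceiling depends on the number analysed: 1/30 = 3.3% at 17 per arm, 1/20 = 5.0% at 12 and 1/16 = 6.2% at 10.

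**Ratio of ANCOVA to final values** (any k): 0.91 × 1.042 = 0.948 at r = 0.3; 0.75 × 1.042 = 0.781 at r = 0.5; 0.36 × 1.042 = 0.375 at r = 0.8. These are cuts of 5%, 22% and 63%.

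**Ratio of ANCOVA to change scores:**

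| k | r = 0.3 | r = 0.5 | r = 0.8 |
|---|---|---|---|
| 0.5 | 0.998 | 1.042 | 0.833 |
| 0.7 | 0.886 | 0.989 | 1.014 |
| 1.0 | 0.677 | 0.781 | 0.938 |
| 1.5 | 0.403 | 0.446 | 0.441 |

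At k = 1 the ratio is (1 + r)/2 × 25/24, so the cuts are 32%, 22% and 6%. It reaches 1 when (1 + r)/2 = 24/25, that is at r = 0.92. At r = 0.95 ANCOVA loses 1.6%. Simulation with 40,000 trials per setting, equal SDs and 14 per arm gave ratios of 0.674, 0.777, 0.937 and 1.012 at r = 0.3, 0.5, 0.8 and 0.95.

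**Why k below 1 matters here.** Entry requires "fasting glucose between 100 and 125 mg/dL" and a 2-hour value of 140 to 199 mg/dL. This truncates the baseline but not the 12-month value. At r = 0.8, ANCOVA is slightly worse than change for any k from 0.68 to 0.92.

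**Power, for scale only.** Take a hypothetical true effect of 1.10 follow-up SD, at which the final-value test has 80% power. The plan powers no continuous outcome.
- At k = 1, final / change / ANCOVA give 80/66/82% (r = 0.3), 80/80/89% (r = 0.5) and 80/99.3/99.5% (r = 0.8).
- Over the four values of k in the table, the change test ranges over 45–82%, 56–90% and 86–99.6%. ANCOVA stays at 82%, 89% and 99.5%.
- The largest ANCOVA shortfall on this grid is 1.3 points, against change at k = 0.5, r = 0.5.

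**The case against.** The strongest reply is that nothing here is invalid. Under randomization the final-value test and the change test are each unbiased and hold their 5% level. A between-arm comparison of change answers the before-and-after goals. The trial is sized on proportions, which ANCOVA does not touch. The gain over the better unadjusted test may be small: at k = 1 and the hypothetical effect it is about 2, 9 and 0.2 points. All of this stands, and it is why the point is an improvement and not an error.

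Four stronger readings are tempting and are not supported:
- **The unadjusted tests bias the result or inflate type I error.** They do not. Reporting whichever of the two is significant would raise the error rate to about 9% (simulation, equal SDs), but the plan does not say it will do this.
- **Equal SDs alone give a 6–32% gain.** That range also needs r between 0.8 and 0.3 and 14 analysed per arm. With equal SDs and r from 0 to 1, the result runs from a 48% cut to a loss of about 4%.
- **Every baseline is confirmed as pre-randomization.** For HbA1c this is only inferred from its being measured at the beginning of the study.
- **Twelve months is the settled time point.** Sample size refers to improvement at 6 months.

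The figures assume normal data and a linear relation to baseline. None was computed for log-scale or rank analyses.

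**Conclusion.** The point holds as a loss of precision. The plan uses no baseline covariate and leaves its delta analysis undefined, while most of the needed baselines are scheduled before randomization. At 14 analysed per arm, the price of ANCOVA is bounded at about 4% in variance (roughly 2% in standard error). The possible gain is much larger, but its size rests on an assumed correlation and SD ratio. For the glucose outcomes restricted at entry, the gain over change scores may be nil or slightly negative. The case for ANCOVA is that it is close to or better than the better unadjusted test in every case computed, without knowing r or k beforehand. It is a cheap improvement.

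**What to change.** Change the Statistic analysis wording as follows.

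1. For each continuous outcome with a pre-randomization baseline, make the deciding analysis an ANCOVA of the 12-month value on arm plus that outcome's own baseline.
2. Use the log scale for strictly positive, skewed outcomes (HOMA-IR, Matsuda, cytokines), and state the scale for the other indices, such as QUICKI and HOMA-B.
3. The two increment-ratio beta-cell indices (Dependent variables, items 3 and 4) can be negative or have near-zero denominators. Name one rank method for them, for example regressing the ranked 12-month value on arm and the ranked baseline.
4. Define the delta analysis as the between-arm comparison of change from baseline, and keep it as a sensitivity analysis.
5. Keep the t or Mann-Whitney test for outcomes without a baseline.
6. Confirm that HbA1c is drawn before randomization.
7. Reconcile the time point. The Specific goals, the intervention definition, the glucose-metabolism outcome and the final measurements all point to 12 months; Sample size uses 6 months.

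This does not choose a primary outcome, which is a separate matter. The cost is one degree of freedom and an assumed linear relation to baseline, with no extra patients, visits or samples beyond those planned.

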## **ETHICAL CONSIDERATIONS**

In order to carry out this research, ethical standards, the Regulation of the General Health Law on Health Research and the Declaration of Helsinki of the World Medical Association of the 64th General Assembly, Fortaleza, Brazil in 2013 and International codes and standards in force for good clinical research practices. Special attention will be given to taking care of the privacy and autonomy of the patient. Once the patient has been informed about the study and agrees to participate in it, and since this implies a risk greater than the minimum, the signature of an informed consent letter will be requested (Annex 1).

The protocol was evaluated and approved by the Research Ethics Committee of the Regional High Specialty Hospital of Bajío and the Research Ethics Committee of the University of Guanajuato.

## **HUMAN, MATERIAL AND FINANCIAL RESOURCES**

This work will be carried out in collaboration with Researchers of the Metabolism Laboratory of the Division of Health Sciences of the University of Guanajuato, Campus León, and therefore will be developed both at the University of Guanajuato and at the High Specialty Regional Hospital del Bajío (HRAEB). Patients will be recruited from the

first contact clinics of the SSA and in the outpatient clinic of the Endocrinology, Internal Medicine and Nutrition services of the HRAEB. The drug will be provided by the HRAEB, as well as the analysis of glycosylated hemoglobin. The oral glucose tolerance curve will be carried out with the inputs of the Metabolism Laboratory of the Division of Health Sciences of the University of Guanajuato, Campus León.

## DECLARATION OF CONFLICT OF INTEREST

There is no conflict of interest since the main commitments and obligations of this project are not influenced by other material or personal interests. The medication will be provided by the Bajío High Specialty Hospital

